9.5 Discontinuation of Modakafusp Alfa Treatment and Patient Replacement

Treatment must be permanently discontinued if any of the criteria detailed in Section [8.6.4](#) are met.

Once study drug has been discontinued, all study procedures outlined for the EOT visit will be completed as specified in [Appendix A](#). The primary reason for study drug discontinuation will be recorded on the eCRF.

During Cycle 1 of the dose escalation phase, patients who are discontinued prematurely for reasons other than a DLT will be replaced.

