6.1.1 Phase 1b Single-Agent Dose Escalation

Phase 1b will enroll patients with advanced/metastatic solid tumors that have no standard therapeutic option, are intolerant to those therapies, or have refused them.

The modakafusp alfa SA dose escalation phase is designed to determine the SA RP2D and schedule of modakafusp alfa for further testing. The single-agent RP2D may be either the MTD based on DLTs or a PAD defined by the PK/pharmacodynamic model or exposure-response (ER) analysis in place.

A minimum of 3 patients will be enrolled in the starting dose cohort of modakafusp alfa 0.1 mg/kg administered Q3W. Doses will be escalated as follows: 0.1, 0.2, 0.4, 0.75, 1.5, 3 and 6 mg/kg. Patients will be assessed for DLTs until Cycle 2 Day 1 (C2D1) can be administered from a safety

standpoint. If there are no DLTs in the first cohort of 3 evaluable patients dosed at 0.1 mg/kg, Bayesian Logistic Regression Model (BLRM) guided by the Escalation with Overdose Control (EWOC) principle will be used in successive dose escalation cohorts to estimate the next dose level. More conservative dose escalation, evaluation of intermediate doses, and expansion of an existing dose level are all permissible following discussions between the sponsor and the investigators, if such measures are needed for patient safety or for a better understanding of the dose-related toxicity, exposure, or pharmacodynamics. It is estimated that approximately 30 patients will be enrolled until either the MTD and/or PAD is identified.

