6.1.2 Phase 2 Dose Expansion

Enrollment into phase 2 expansion in combination with pembrolizumab will be initiated once the RP2D of modakafusp alfa has been determined in phase 1b.

The combination treatment cohorts will begin with a single safety-lead in period to evaluate safety and tolerability during the Cycle 1 DLT evaluation period of modakafusp alfa with pembrolizumab. If there are no DLTs in the first 3 patients during Cycle 1 of the safety lead-in period with modakafusp alfa SA RP2D in combination with pembrolizumab 400 mg Q6W, the combination dose and regimen could be selected for the 3 disease cohorts described below. If there is 1 DLT in the initial 3 patients in the safety-lead in period, an additional 3 patients will be enrolled at the same modakafusp alfa RP2D in combination with pembrolizumab 400 mg Q6W. If there are ≥ 2 DLTs in the first 3 patients at the modakafusp alfa SA RP2D, enrollment will resume at the next lower dose level of modakafusp alfa RP2D in combination with pembrolizumab. Other approved pembrolizumab dosing regimens (eg, 200 mg Q3W) could be tested in the safety-lead in period if 400 mg Q6W in combination with modakafusp alfa at one dose lower than RP2D is intolerable.

For the safety lead-in period, patient enrollment will be staggered between the first and second patients by 7 days. The second and third patients can be dosed concurrently if the first patient in the cohort has gone through the Day 8 visit without clinically significant acute toxicities. Patients enrolled in the safety lead-in phase could have any of the 3 melanoma disease categories described below.

Following completion of the safety lead-in phase and review of safety data, phase 2 of the study will further explore the safety and efficacy of modakafusp alfa treatment in combination with pembrolizumab. The combination cohorts, including patients in the safety-lead phase, will enroll patients with unresectable/metastatic melanoma in the following subgroups:

- I. Unresectable/metastatic cutaneous melanoma with primary resistance to no more than 2 prior lines of anti-PD1 containing treatments in the metastatic setting.
- II. Unresectable/metastatic cutaneous melanoma with acquired resistance to no more than 2 prior lines of anti-PD1 containing treatments in the metastatic setting.
- III. Unresectable/metastatic cutaneous melanoma naïve to prior anti-PD1 containing treatments in the metastatic setting.

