8.3 Phase 1b Modakafusp Alfa SA Dose Escalation Schema

The 2-parameter BLRM implementing the EWOC principle will be used to inform dose escalation decisions and MTD estimation starting from the second dose cohort. The final decision on next dose level will be taken jointly by the sponsor and the participating investigators.

BLRM with overdose control ([Appendix E](#)) will be used to inform dose escalation decisions and MTD estimation, along with consideration of other emerging safety, clinical, PK, and pharmacodynamic data. Doses will be escalated as shown in [Table 8.a](#).

Table 8.a **Planned Dose Levels**

Dose Level	Dose (Unit)
-1	0.05 mg/kg
1	0.1 mg/kg
2	0.2 mg/kg
3	0.4 mg/kg
4	0.75 mg/kg
5	1.5 mg/kg
6	3.0 mg/kg
7	6.0 mg/kg

More conservative dose escalation, evaluation of intermediate doses, and expansion of an existing dose level are all permissible following discussions between the sponsor and the investigators, if such measures are needed for patient safety or for a better understanding of the dose-related toxicity, exposure, or pharmacodynamics. The initial size of each cohort will be approximately 3 evaluable patients.

Initially, 3 patients will be enrolled at the 0.1 mg/kg starting dose level. The following rules will be used only for this initial cohort:

- If none of the 3 patients experiences a DLT during the first cycle, the dose may be escalated to the next planned dose level.
- If 1 of the 3 patients exhibits a DLT, then the cohort will be expanded from 3 patients to a total of 6 patients.
 - If no more than 1 patient out of the 6 total patients has a Cycle 1 DLT, 3 patients will be enrolled at the next dose level.
 - If 2 of the 6 patients have a Cycle 1 DLT, 3 additional patients will be enrolled. If any of the 3 additional patients have a Cycle 1 DLT, the starting dose will be considered not tolerated and the dose will be de-escalated to 0.05 mg/kg. If none of the 3 additional patients have a Cycle 1 DLT, the starting dose may be considered the MTD or may be escalated to the next dose level, after consideration of other available safety, clinical, PK, and pharmacodynamic data.
 - If 3 or more of the 6 patients experience a Cycle 1 DLT, the starting dose level will be considered not tolerated and the dose will be de-escalated 0.05 mg/kg following review of all available safety data and approval of the sponsor.

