8.4 Phase 2 Modakafusp Alfa Dose Expansion

A minimum of 3 patients will be enrolled at the modakafusp alfa RP2D in combination with pembrolizumab 400 mg Q6W to evaluate safety and tolerability in a single safety lead-in phase. The safety lead-in phase will start with the enrollment of 3 initial patients to evaluate the tolerability during the Cycle 1 DLT evaluation period of modakafusp alfa with pembrolizumab. If there are no DLTs in the first 3 patients during Cycle 1 of the safety lead-in period with modakafusp alfa SA RP2D in combination with pembrolizumab 400 mg Q6W, the combination dose and regimen could be selected for the 3 melanoma disease cohorts.

If there is 1 DLT in the initial 3 patients in the safety-lead in period, an additional 3 patients will be enrolled at the same modakafusp alfa RP2D in combination with pembrolizumab 400 mg Q6W. If there are ≥ 2 DLTs in the first 3 patients at the modakafusp alfa SA RP2D, enrollment will resume at the next lower dose level of modakafusp alfa RP2D in combination with pembrolizumab. Other approved pembrolizumab dosing regimens (ie, 200 mg Q3W) could be tested in the safety-lead in period if 400 mg Q6W in combination with modakafusp alfa at one dose lower than RP2D is intolerable. For the safety lead-in period, patient enrollment will be staggered between the first and second patients by 7 days in the first dose cohort. The second and third patients can be dosed concurrently if the first patient in the cohort has gone through the Day 8 visit without clinically significant acute toxicities. Subsequent cohorts, if any, will not require staggering between patients.

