7.3 Analysis Sets

- Safety Analysis Set: The safety analysis set will include all enrolled patients who received at least one dose (even incomplete) of the study drug.
- Response evaluable Analysis set: The response evaluable analysis set is a subset of the safety analysis set including patients with measurable disease at baseline and at least 1 post-treatment evaluation.
- DLT Evaluable Analysis Set: patients who receive all Cycle 1 doses of modakafusp alfa or experience a DLT in Cycle 1 in the dose-escalation portion of the study; or patients who receive all Cycle 1 doses of modakafusp alfa in combination with pembrolizumab or experience a DLT in Cycle 1 in the safety lead-in portion of the study.
- Pharmacokinetic Analysis Set: patients from the safety analysis set who have sufficient data to calculate at least 1 PK parameter for modakafusp alfa.
- Immunogenicity-evaluable Analysis Set: Includes patients with a baseline and at least one post-baseline immunogenicity assessment.

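### The safety lead-in counts the first 3 patients rather than 3 evaluable patients, and replacement is provided only in dose escalation, so the combination could be selected with fewer than 3 patients fully observed for DLTs

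*Protocol*

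**What the plan says.** Replacement. Protocol 9.5 reads: "During Cycle 1 of the dose escalation phase, patients who are discontinued prematurely for reasons other than a DLT will be replaced". No section gives a corresponding rule for the lead-in. Protocol 8.2, by contrast, names both the escalation phase and the combination safety lead-in when it defines DLTs.

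Decision unit in phase 1b. Protocol 6.1.1 conditions the first escalation step as follows: "If there are no DLTs in the first cohort of 3 evaluable patients dosed at 0.1 mg/kg". Protocol 8.3 adds: "The initial size of each cohort will be approximately 3 evaluable patients".

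Decision unit in the lead-in. Protocol 8.4 begins: "A minimum of 3 patients will be enrolled at the modakafusp alfa RP2D". The clearing condition is "If there are no DLTs in the first 3 patients during Cycle 1 of the safety lead-in period", and if it is met, "the combination dose and regimen could be selected for the 3 disease cohorts described below" (Protocol 6.1.2). Protocol 2.0 and SAP 4.1 carry the same rule. None of these four places uses the word evaluable.

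Analysis set. SAP 7.3 defines a DLT-evaluable set that covers the lead-in: "patients who receive all Cycle 1 doses of modakafusp alfa in combination with pembrolizumab or experience a DLT in Cycle 1". It is used for the escalation posterior summary (SAP 7.1) and the by-patient DLT listing (SAP 7.12.1). Neither document links it to the lead-in decision.

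**The concern.** A small DLT rule is informative only if each patient counted was at risk for the whole DLT period. Several criteria in Protocol 8.2 need time to appear: Grade 4 neutropenia beyond 7 days, Grade 3 or higher thrombocytopenia beyond 14 days, and a Cycle 2 delay of more than 14 days. A patient who leaves in the second week without a DLT cannot show these. If that patient still counts among the first 3, the result looks like 0 of 3 but carries less information.

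The lead-in is the one formal DLT check on the combination before three cohorts of up to 25 open. Protocol 4.3.5 presents it as the means of limiting overlapping toxicity and says that no nonclinical toxicology study of the combination was done. Phase 2 uses a different formulation of modakafusp alfa from phase 1b (Protocol 8.12), and there is no external data safety monitoring committee (Protocol 11.0).

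**Working it through.** **The plan's own figure.** Three cohorts of 25 give 3 × 25 = 75 expansion patients. With up to 9 lead-in patients, 75 + 9 = 84, the phase 2 maximum in Protocol 13.1.2. With about 30 in phase 1b, 84 + 30 = 114, as in Protocol 6.2. The documents give no operating characteristics for the lead-in rule, so there is no such figure to reproduce.

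**Does SAP 7.3 protect the rule?** Membership needs all Cycle 1 doses or a Cycle 1 DLT. Table 16.d schedules both drugs in Cycle 1 on Day 1 only. A patient who receives both infusions and withdraws or progresses on Day 8 has therefore had all Cycle 1 doses and is DLT-evaluable under the SAP. The set excludes only missed or incomplete Day 1 dosing without a DLT, and it does not say whether a partial infusion is a dose received.

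**Chance of no DLT.** With true DLT rate p and k fully observed patients, P(0 DLTs) = (1 − p)^k. The exact one-sided 95% upper limit after 0 of k is 1 − 0.05^(1/k). The value p = 0.33 is the phase 1b overdose threshold (Protocol 8.3); the lead-in states no target rate. The values 0.40 and 0.50 are illustrative.

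| Fully observed | p = 0.33 | p = 0.40 | p = 0.50 | Upper limit after 0 DLTs |
|---|---|---|---|---|
| 3 | 0.301 | 0.216 | 0.125 | 63.2% |
| 2 | 0.449 | 0.360 | 0.250 | 77.6% |
| 1 | 0.670 | 0.600 | 0.500 | 95.0% |

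For example, 0.67³ = 0.301 and 0.67² = 0.449.

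**Averaged over loss.** Let q be the chance that a patient is lost to DLT assessment without a DLT. The documents give no value; 5% to 20% is an assumption. At least one of 3 is lost with probability 1 − (1 − q)³, and two or more with probability 3q²(1 − q) + q³. If lost patients count as DLT-free and loss is independent of toxicity, P(0 DLTs among the first 3) = (1 − (1 − q)p)³.

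| q | At least 1 lost | 2 or more lost | P(0 DLTs), p = 0.33 | P(0 DLTs), p = 0.50 |
|---|---|---|---|---|
| 0 (all replaced) | 0 | 0 | 0.301 | 0.125 |
| 0.05 | 0.143 | 0.007 | 0.324 | 0.145 |
| 0.10 | 0.271 | 0.028 | 0.347 | 0.166 |
| 0.20 | 0.488 | 0.104 | 0.399 | 0.216 |

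For q = 0.20 and p = 0.33: (1 − 0.8 × 0.33)³ = 0.736³ = 0.399. The chance of 2 or more DLTs in 3, which sends the lead-in to a lower dose level, falls at p = 0.33 from 0.255 to 0.233 (q = 0.05) or 0.172 (q = 0.20).

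Both calculations treat a lost patient as contributing no information. One who leaves part-way could already have shown an early DLT, so for such patients these figures are the outer edge of the effect.

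**The case against.** - **Silence is not a rule.** A reader might infer that lead-in patients lost in Cycle 1 are not replaced and must count. No section says either. Protocol 13.1.2 speaks of 3 to 9 patients being evaluated during their first cycle, which leans the other way. This stands, and the point is limited to what a literal reading permits. Nor is the phrase plainly shorthand: Protocol 8.3 also says simply 3 patients in its starting-dose rules, but there the cohort size is stated as evaluable and 9.5 provides replacement. The lead-in has neither.
- **Zero DLTs is not an automatic go.** The regimen could be selected, and expansion follows a review of safety data (Protocol 6.1.2). DLT-type events in later cycles or in expansion bear on the recommended dose (8.2), and enrolment-hold thresholds continue (8.5). This stands, but none of these sets a minimum number of fully observed lead-in patients.
- **A patient who leaves on Day 8 creates no conflict with the SAP.** A reader might infer that the decision and the SAP set would disagree on that patient. They would not, because SAP 7.3 counts the patient as evaluable. For the same reason, a fix that merely cites SAP 7.3 would fail.
- **Infusion reactions do not establish the loss rate.** Eight of 17 phase 1b patients had Grade 2 reactions, but Table 8.e allows restart, premedication is now mandatory (8.8.1), and no count of incomplete Cycle 1 infusions is given. A related Grade 2 nonhematologic toxicity judged dose-limiting is itself a DLT (8.2). The median of 2 cycles (4.3.2.2) does not show how many left during Cycle 1 without a DLT. This stands, so q remains an assumption.

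**Conclusion.** The point holds as a gap in a stated decision rule. Replacement covers escalation only, the lead-in counts patients without requiring evaluability, and SAP 7.3 neither governs the decision nor requires observation to the end of the DLT period. The combination could therefore be selected on fewer than 3 fully observed patients. The documents do not support saying that this must happen.

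The average effect is modest: at a true rate of 33%, a gain of 2.3 to 9.8 percentage points in the chance of a zero-DLT result for an assumed loss of 5% to 20%. It is substantial when a patient is actually lost: 45% against 30%, with the upper limit moving from 63% to 78%. The single-patient case needs two of three lost, and two or more losses have a chance of 0.7% to 10.4% over that range. All of this rests on the borrowed 0.33 benchmark, the assumed loss rate, and loss unrelated to toxicity. The change should be made because it is cheap and brings the lead-in to the standard already set for phase 1b.

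**What to change.** 1. Protocol 9.5: extend the replacement rule to Cycle 1 of the safety lead-in.
2. Protocol 2.0, 6.1.2 and 8.4 and SAP 4.1: wherever the lead-in rule refers to the first, initial or additional 3 patients, make it the same number of DLT-evaluable patients.
3. SAP 7.3: define DLT-evaluable as having a Cycle 1 DLT, or having received the Cycle 1 doses and been observed through the Cycle 1 DLT period of Protocol 8.2. State whether a partial infusion counts as a dose received. Without this step, items 1 and 2 would replace a patient whom the SAP still counts as evaluable.
4. State whether replacements count toward the 3 to 9 lead-in patients, since the total of 84 depends on it.

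Every treated patient stays in the safety analysis set. The DLT criteria and doses are untouched. The cost is a few words in each document, an occasional replacement patient and a short delay to the lead-in decision.

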9.6 Study Compliance

Study drug will be administered or dispensed only to eligible patients under the supervision of the investigator or identified subinvestigator(s). The appropriate study personnel will maintain records of study drug receipt and dispensing.

9.7 Posttreatment Follow-up Assessments (PFS and OS)

Patients who stop treatment for any reason other than PD will continue to have PFS follow-up visits. The PFS follow-up should occur every 12 ± 1 weeks from the EOT until the occurrence of progression, death, the start of subsequent systemic antineoplastic therapy, study termination, or until 6 months after the discontinuation of study treatment, whichever occurs first.

After disease progression or starting another systemic anticancer therapy, all patients will be followed every 12 ± 1 weeks for OS until death or study termination. Survivor information and death details may be collected by methods that include, but are not limited to, telephone, e-mail, mail, or retrieval from online or other databases (eg, Social Security indexes). In addition, the start of another anticancer therapy for the disease under study will be collected.

See [Appendix A](#) for appropriate assessments during follow-up.

NOTE: Treatment-related SAEs must be reported to the Global Pharmacovigilance department or designee. This includes deaths that the investigator considers related to study drug that occur during the posttreatment follow-up. Refer to Section [10.0](#) for details regarding definitions, documentation, and reporting of SAEs.

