6.3 Duration of Study

6.3.1 Duration of an Individual Patient's Study Participation

Patients may receive modakafusp alfa as a SA for up to 1 year or in combination with pembrolizumab for up to 2 years. Patients with demonstrated clinical benefit can continue treatment beyond those points if approved by the sponsor. These patients can continue receiving treatment in this study or in any of the poststudy access modalities described in the protocol (Section 6.3.5). Patients may discontinue treatment when they meet any of the discontinuation criteria stated in the protocol (Section 9.6).

All patients will have an EOT visit 30 days (+10 days) after receiving the last dose of study drug or before the start of subsequent systemic anticancer therapy, whichever occurs first, to permit detection of any delayed TEAEs and to resolve any ongoing events. Patients with unresolved TEAEs will continue the periodic safety follow-up until complete resolution or stabilization (established as sequelae) occurs.

Patients who discontinue study treatment for reasons other than progressive disease (PD) will continue PFS follow-up every 12 ± 1 weeks from the EOT visit until the occurrence of PD, lost to follow-up, consent withdrawal, death, start of subsequent systemic anticancer therapy, or study termination, whichever occurs first. After disease progression or starting another systemic anticancer therapy, all patients will be followed every 12 ± 1 weeks for OS until death or study termination.

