13.4 Efficacy Analysis

Efficacy endpoints include ORR, DCR, DOR, PFS, and OS. No formal statistical tests will be performed for these efficacy endpoints.

ORR is defined as the proportion of patients who achieve CR or PR (determined by the investigator) during the study in response-evaluable population.

DCR is defined as the proportion of patients who achieve CR, PR, or SD (determined by the investigator) during the study in response-evaluable population.

DOR is the time from the date of first documentation of a PR or better to the date of first documentation of PD for responders (PR or better). Responders without documentation of PD will be censored at the date of last response assessment that is SD or better.

TTP is the time from the date of the first dose of study drug to the date of the first documentation of PD according to RECIST v1.1.

PFS is defined as the time from the date of the first dose of study drug to the date of first documentation of PD according to RECIST v1.1 or death due to any cause, whichever occurs first. Patients without documentation of PD or death will be censored at the date of the last response assessment that is SD or better.

OS is defined as the time from the date of first dose of study drug to the date of death due to any cause. Patients without documentation of death at the time of analysis will be censored at the date last known to be alive.

ORR and DCR will be summarized using descriptive statistics with 95% CIs. PFS and OS will be analyzed descriptively using the Kaplan-Meier method for the safety analysis set. DOR will also be analyzed using the Kaplan-Meier method for the response-evaluable analysis set.

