- ^t Patients will be followed for survival every 12±1 weeks until death, loss to follow-up, consent withdrawal, or study termination. Survivor information and death details may be collected by methods that include, but are not limited to, telephone, e-mail, mail, or retrieval from online or other databases (eg, Social Security indexes). In addition, the start of another anticancer therapy for the disease under study will be collected.

16.4 Table 16.d Schedule of Events: Screening, Baseline, Cycle 1, Cycle 2, and Cycle 3 (Phase 2 Dose Expansion)

Table 16.d Schedule of Events: Screening, Baseline, Cycle 1, Cycle 2, and Cycle 3 (Phase 2 Dose Expansion)

Study Period or Treatment Cycle	Screening	Cycle 1						Cycle 2		Cycle 3						
		Day <21	Day 1	Day 2	Day 3	Day 4	Day 8	Day 15	Day 1	Day 2	Day 1	Day 2	Day 3	Day 4	Day 8	Day 15
Window Allowed		0	0	0	0	±2 d	±2 d	±2 d	0	±2 d	±0 d	0	0	±2 d	±2 d	
Informed consent ^a	X															
Eligibility criteria	X															
Demographics	X															
Medical history	X															
Prior medication and treatment history	X															
Height (screening only) and weight	X							X		X						
ECOG performance status	X	X						X		X						
12-lead ECG ^b	X	X						X		X						
Triplicate 12-lead ECG ^b		(X)	(X)													
Physical examination	X	X						X		X						
Vital signs ^c	X	X						X		X						
Monitoring of concomitant medication/procedures	Recorded from signing of the ICF through 30 days after last dose of study drug or the start of subsequent anticancer therapy, whichever occurs first.															
AE reporting	Recorded from signing of the ICF through 30 days after last dose of study drug or the start of subsequent anticancer therapy, whichever occurs first. The reporting period for irAEs is extended to 90 days after administration of the last dose of study drug or the start of subsequent anticancer therapy, whichever occurs first, and recorded in the eCRFs.															
	SAEs will be reported from signing of ICF through 30 days after last dose of study drug even if the patient starts nonprotocol systemic therapy. Serious irAEs will be reported through 90 days after last dose of study drug.															
Dosing																
Modakafusp alfa infusion ^d		X							X		X					
Pembrolizumab infusion ^e		X									X					
Disease Assessment																
CT/MRI scans ^f	X	Repeat every 6 weeks through Cycle 6 then every 9 weeks thereafter.														

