probability estimates with 95% CIs at 3 and 6 months (or later time points if data permits) will be presented. The number of patients with events along with the type of events (death or progressive disease) and the number of patients censored will be summarized.

PFS for all patients in the safety analysis set will be listed.

Overall Survival (OS)

Overall survival in months is defined as the time from the date of first dose to the date of death of any cause [OS (months) = (date of death or censor – date of first dose + 1)/30.4375]. Patients without documentation of death at the time of analysis will be censored at the date last known to be alive.

The analysis of OS will be based on the safety analysis set with a reasonable number of patients. The Kaplan-Meier method will be used to analyze the distribution of OS. Kaplan-Meier survival curves, the 25th, 50th (median), and 75th percentiles, along with associated 2-sided 95% confidence intervals (CIs) based on Brookmeyer and Crowley method, and Kaplan-Meier estimates with 95% CIs at 6 and 12 months (or later time points if data permits) will be presented. The number of patients with events and the number of patients censored will be summarized.

OS for all patients in the safety analysis set will be listed.

Time to Progression (TTP)

Time to progression is defined as the time from first dose to the date of first documentation of objective progression. Patients without documentation of PD (iCPD) will be censored at the date of the last response assessment that is SD or better prior to the date of initiation of alternative anti-cancer therapy. Patients with no post baseline response assessment will be censored on day 1.

$TTP \text{ (months)} = (\text{date of progression or censor} - \text{date of first dose} + 1) / 30.4375$.

The Kaplan-Meier method will be used to estimate the distribution of TTP with a reasonable number of patients in the response evaluable set. Kaplan-Meier curves, the 25th, 50th (median), and 75th percentiles, along with associated 2-sided 95% confidence intervals (CIs) based on Brookmeyer and Crowley, and Kaplan-Meier estimates with 95% CIs at 3 and 6 months (or later time points if data permits) will be presented. The number of patients with events and the number of patients censored will be summarized.

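### Section 9.7 caps PFS follow-up at 6 months off treatment but starts OS follow-up only at progression or new therapy, so progression-free patients drop out of survival follow-up that Appendix A requires

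*Protocol*

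**What the plan says.** Protocol Section 9.7 gives patients who stop treatment without progression 12-weekly PFS visits until progression, death, new systemic therapy, study termination, "or until 6 months after the discontinuation of study treatment, whichever occurs first". The PFS footnotes in Appendix A (s in phase 1b, t in phase 2) carry the same cap. Section 9.7 then starts survival follow-up with "After disease progression or starting another systemic anticancer therapy, all patients will be followed every" 12±1 weeks.

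Section 6.3.1 uses the same survival trigger but no cap. There, PFS follow-up runs "until the occurrence of PD, lost to follow-up, consent withdrawal, death, start of subsequent systemic anticancer therapy, or study termination, whichever occurs first".

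The Appendix A survival footnotes (t in phase 1b, u in phase 2) say "Patients will be followed for survival every" 12±1 weeks until death, loss to follow-up, consent withdrawal or study termination. They do not mention progression or new therapy.

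For analysis, protocol Section 13.4 says that patients without a documented death "will be censored at the date last known to be alive", and SAP Section 7.9 repeats the rule. The SAP plans Kaplan-Meier quartiles including the median, and "estimates with 95% CIs at 6 and 12 months (or later time points if data permits"). Section 13.4 adds: "No formal statistical tests will be performed for these efficacy endpoints".

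**The concern.** Under 9.7 a patient who stops for toxicity, complete response or completed treatment, and who is progression-free and untreated 6 months later, has left PFS follow-up without meeting the OS trigger. The footnotes require survival contact for the same patient, so a site cannot tell from the text which rule applies.

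If sites follow 9.7, whether a patient's OS is censored early depends on remaining progression-free. Kaplan-Meier estimation assumes that censored patients have the same later death hazard as those still at risk. Patients 6 months off treatment without progression probably have a lower one, and removing them leaves the later part of the curve to patients with poorer prognosis.

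**Working it through.** **The rules side by side**

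| Place | PFS follow-up capped at 6 months? | Survival follow-up needs progression or new therapy? |
|---|---|---|
| Section 6.3.1 | No | Yes |
| Section 9.7 | Yes | Yes |
| PFS footnotes (s phase 1b, t phase 2) | Yes | Not addressed |
| Survival footnotes (t phase 1b, u phase 2) | Not addressed | No |

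Take a patient who stops at month *m*, with no progression and no new therapy.

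- Section 6.3.1 alone: the patient stays under 12-weekly contact until progression or new therapy, either of which opens OS follow-up. The other endings leave nobody to follow. There is no gap.
- Section 9.7: PFS follow-up ends at *m* + 6 with the OS trigger unmet. No visit is then scheduled at which a later progression or new therapy would be learned.
- Survival footnotes: contact continues. There is no gap.

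The gap needs the cap and the trigger together, and only 9.7 has both.

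**Last scheduled contact under 9.7**

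Section 6.3.1 sets the EOT visit: "All patients will have an EOT visit 30 days (+10 days) after receiving the last dose of study drug", that is, day 30 to 40. Visits every 12±1 weeks are 77 to 91 days apart.

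- First visit: 30 + 77 = 107 to 40 + 91 = 131 days after last dose.
- Second visit: 30 + 154 = 184 to 40 + 182 = 222 days.
- Cap, if counted from last dose: 6 × 30.4375 = 182.6 days.

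On that count the second visit falls after the cap, and the last contact may be only about 4 months after last dose. If discontinuation were dated at EOT, the second visit (154 to 182 days later) would just fit.

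**Size**

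The documents give no OS rate, event target or power, so there is no plan figure to reproduce. An illness-death simulation (400,000 patients) compared OS with everyone followed against censoring 6 months after a progression-free stop. All rates are assumptions:

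- median time to progression 3, 6 or 12 months, with median survival after progression of 9, 12 or 18 months respectively;
- 20% or 50% stopping by month 24 by a constant hazard, and everyone stopped by then;
- with or without 30% long-term controllers (one-fifth the progression hazard);
- death hazard while progression-free 0.002 per month;
- data cut-off at 25 to 43 months.

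Selected results (% alive; everyone followed → 9.7 rule):

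| Median time to progression / survival after it (months) | Stop by 24 mo | Controllers | In gap | 12 mo | 24 mo | 36 mo | Median OS (mo) |
|---|---|---|---|---|---|---|---|
| 3 / 9 | 20% | none | 1.0% | 55.9 → 55.8 | 23.2 → 23.1 | 9.2 → 9.2 | 13.6 → 13.6 |
| 6 / 12 | 50% | 30% | 22.4% | 79.1 → 78.6 | 52.8 → 50.4 | 34.2 → 27.8 | 25.5 → 24.2 |
| 12 / 18 | 50% | 30% | 37.1% | 89.7 → 89.4 | 73.0 → 70.9 | 57.0 → 48.8 | 41.9 → 35.3 |

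Over all 12 combinations the 6-month estimate did not move. The shortfall was 0.1 to 0.5 points at 12 months, 0.1 to 2.4 at 24 and 0 to 8.2 at 36. The median was 0 to 6.6 months lower.

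Three variations:

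- Last row, last contact at 3.75 months (day 30 + 84 = 114): 36-month OS is 46.7% against 57.0%.
- Last row, half of the gap patients still traced: 54.2% against 57.0%.
- Reversal: with a progression-free death hazard of 0.06 per month (medians 12 and 36 months, 50% stopping, no controllers), 24-month OS is 40.3% under 9.7 against 39.3% with everyone followed.

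**The case against.** The strongest reply is that the protocol already covers these patients. Section 9.7 refers to Appendix A for follow-up assessments, and Appendix A has no trigger. Section 9.4 does not list the cap among the events that complete the study, so the patient is formally still on study. Section 9.7 also lets vital status be taken from telephone contact or databases. OS is secondary and descriptive, and the SAP's two named landmarks hardly move. In the phase 1b data at the January 2021 cutoff, progression was the reason for 75.0% of treatment discontinuations (Section 4.3.2.2), and those patients go straight into OS follow-up.

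Most of this stands as a limit on size. It does not remove the conflict: 9.7 still states its own condition for OS follow-up, a cross-reference does not say which rule prevails, and database retrieval is only permitted. The omission from Section 9.4 leaves the patient neither completed nor scheduled for contact.

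Two stronger readings are tempting. A reader might infer that 6.3.1 also loses these patients, because its trigger is worded the same. It does not, because it has no cap. A reader might also infer a large error at 24 months. Suppose 20% stop progression-free with 10% annual mortality, all are lost at month 12, and the rest have exponential OS with median 12 months. Then:

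- S(12) = 0.2 × 0.9 + 0.8 × 0.5 = 0.58, and the Kaplan-Meier value at 24 months is 0.58 × 0.5 = 29%.
- The true value is 0.2 × 0.81 + 0.8 × 0.25 = 36.2%.

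Varying the share from 10% to 30% and the median from 9 to 12 months gives about 4 to 14 points. With a 6-month cap, that requires every such patient to stop at about month 6. Treatment may run to 1 year (single agent) or 2 years (combination), so completers reach the cap at about month 18 or 30. This is an upper-end scenario, and its mortality figure has no source in the documents.

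**Conclusion.** The conflict is certain on the text: 9.7 leaves progression-free, untreated patients without OS follow-up after the cap, the survival footnotes follow them, and 6.3.1 disagrees with 9.7 on when PFS follow-up ends.

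The effect on OS is an inference. Downward bias in the median and in later Kaplan-Meier estimates is probable, on the assumption that these patients have a lower death hazard than those still at risk. A reader might take the downward direction as established; the documents do not show it, and a high progression-free death hazard reverses it. The size cannot be derived from the plan. On the assumed rates it is negligible at the SAP's 6- and 12-month landmarks and can matter at 36 months and for the median. Tracing patients through records shrinks it. The point should be corrected because it affects a secondary endpoint in both phases.

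**What to change.** In Sections 6.3.1 and 9.7 replace the progression/new-therapy trigger with wording such as: *From EOT, survival status will be collected for every patient at intervals of 12±1 weeks (at, or between, PFS visits while those continue), regardless of progression status, until death, loss to follow-up, withdrawal of consent or study termination.* This agrees with the survival footnotes and closes the gap.

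Starting from EOT matters. A rule that began when PFS follow-up ends would, read literally, omit patients who stop for progression, since they never enter PFS follow-up. Unless it excluded consent withdrawal, it would also cover patients from whom Section 9.4 bars further data.

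Then use one PFS follow-up stopping rule in 6.3.1, 9.7 and the PFS footnotes, so that the cap is either in all of them or in none.

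The cost is a clause in two sections, one aligned stopping rule, and a few extra telephone or record contacts of a kind that 9.7 already allows and the footnotes already require.
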